# 8. STATISTICAL METHODS

# 8.1 Statistical hypotheses

No formal statistical hypotheses were formulated.

# 8.2 Estimation of sample size

No formal sample size calculation was performed. Separate dose escalation (3+3) will be performed in Part 1A Group 1 and Part 1A Group 2.

The purpose of the extension to the phase 2 expansion, introduced in Amendment 12, will be to achieve 2 cohorts of approximately 60 subjects per cohort under phase 2 conditions with and without AR LBD mutations to enable more accurate estimate of PSA response and rPFS, to support phase 3 study design as well as giving balance between the AR LBD mutation negative and positive patient population.

Simon's two-stage design (Simon R, 1989) was used to estimate the number of AR LBD mutation negative mCRPC patients in Part 2 extension (added in Amendment 12). The null hypothesis that the true PSA response rate is 5% will be tested against a one-sided alternative. Criteria for continuation of patient enrolment may be met at any time during the conduct of the study. However, if not met, then in the first stage, 23 subjects will be enrolled. If there are one or fewer PSA responses in these 23 subjects, the study will be stopped, otherwise, enrolment will continue as planned. The null hypothesis will be rejected if six or more PSA responses are observed in 56 patients. This design yields a significance level of 0.05 and power of 80% when the true response rate is 15%.

# 8.3 Analysis populations

The patients will be classified into the following data sets before database lock:

- Intention-to-treat (ITT) population: all enrolled patients, regardless of whether they are later found to be ineligible, a protocol violator, never treated or not evaluated.
- Per-protocol (PP) population: Patients who have completed the study according to the protocol without relevant major protocol deviations. A list of protocol deviations will be prepared. Classification and evaluation of the relevance of major protocol deviations will be made before database lock.
- Safety population: all patients who have received at least 1 dose of study treatment.

The analysed dataset for the primary evaluation in Part 1 will be safety population and in Part 2 primarily ITT population and secondarily PP population. Criteria for different data sets will be defined in the statistical analysis plan.

# 8.4 Statistical analyses

Statistical analyses are described in more detail in the statistical analysis plan.

All evaluations will be performed for observed cases only and data will be presented separately by study part (Part 1, Part 2-), pooled over study parts and by dose level and by AR LBD mutation status, asif appropriate.

Confidence intervals (CIs): A two-sided type I error rate of 0.05 together with estimated 95% CIs will be used in this study.

Missing values and outliers: Statistical analysis will be performed for observed cases only. Possible sensitivity analyses may be carried out to evaluate the robustness of the statistical results, particularly the impact of potential outliers.

Missing event occurrence dates will be imputed as the earliest possible date. Missing event dates e.g., due to withdrawal of consent, lost to follow up or not known to have died at the analysis cut-off date, will be right censored (e.g. using last assessment in the study). Detailed methods are described in the statistical analysis plan.

Data transformations: PK parameters (at least AUC and  $C_{max}$ ) will be analysed after logarithmic transformation and the geometric mean will be calculated. Appropriate transformations may be used to analyse other parameters if found to improve conditions underlying the use of statistical methods.

Baseline is defined as last available measurement before study treatment starts. In case several measurements are taken at baseline, a mean value of measurements is used as a baseline.

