mCRPC patients with or without identified activating mutation(s) in the AR LBD in plasma etDNA were enrolled. A total of 6 out of 31 (19.4%) evaluable patients had a PSA response ( $\geq$  50% decline from baseline). A clear difference in the frequency of PSA responses was seen between the patients with mutated AR LBD and the patients without AR LBD mutation. 4 out of 8 (50%) evaluable patients with activating mutation in the AR LBD had PSA response, and one of them achieved partial radiographic soft tissue response (PR) by RECIST 1.1. A total of 2 out of 23 (8.7%) evaluable patients without activating mutation in the AR LBD had PSA response, and response, and in this patient group radiographic soft-tissue responses remained absent. The mean time on treatment in AR LBD mutation positive patient group was 4.8 months, the longest treatment period was 26 months. No dose response relationship between the ODM 208 dose and antitumour activity was observed.

For further details on ODM-208 and human data from the ongoing clinical study (3124001), see the current ODM-208 Investigator's Brochure.

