# 4.5 Removal of patients from treatment

Study subjects are free to discontinue the study at any time without providing a reason. However, the investigator should try to identify the reason and document it in the CRF.

In general, patient must discontinue the treatment, if the investigator or the sponsor considers the discontinuation to be medically necessary or in the best interest of the patient.

A patient must discontinue the study treatment if any of the following reasons applies:

- An AE(s) that the investigator assesses to be intolerable to the patient and related to study treatment or other toxicity that prevents further administration of study treatment as judged by the investigator. For Part 1/Phase 1 only: See section 3.3.4 for discontinuation criteria in case of a DLT.
- Disease progression as judged by the investigator (after disease progression the treatment may be continued if it is considered clinically beneficial to the patient, as judged by the investigator)
- Sponsor's major safety concern regarding the patient.
- Patient's personal decision to discontinue from the study.
- Withdrawal of consent
- Lost to follow-up.
- Protocol deviation that could affect the outcome of the study, as judged by the investigator.
- If dosing of ODM-208 is interrupted for more than 14 days.
- Sponsor terminates the study; see section 10.4.

Criteria for dosing interruption and modifications are described in section 3.3.5.

Irrespective of the reason for discontinuation, the patient should be invited to end-of-study (EOS) assessments as soon as possible. As long as the patient consents, all relevant assessments, at least those of safety, should be performed, preferably according to the schedule for the EOS assessments.

After discontinuation of ODM-208, administration of substitution treatment with glucocorticoid and fludrocortisone must be continued (see section 3.3.6.1).

The study monitor should be notified about premature discontinuations by email/phone within 24 h in the event of discontinuation due to an SAE (see section 6.5.1.3) or within 7 days in the event of discontinuation due to another reason.

The sponsor will decide if patients who prematurely discontinue will be replaced. Discontinued patients are not allowed to re-enter the study.

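### Section 8.4 restricts every evaluation to observed cases although section 8.3 makes ITT primary in Part 2; response rates are raised whenever a patient is missing, and the two-stage error rate holds only if 23 and 56 mean enrolled, unreplaced patients

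*Protocol*

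**What the plan says.** Protocol section 8.3 defines the ITT population as "all enrolled patients, regardless of whether they are later found to be ineligible, a protocol violator, never treated or not evaluated". It names ITT as the primary set for the main Part 2 evaluation, with PP second.

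Section 8.4 opens its analysis rules with "All evaluations will be performed for observed cases only" and repeats the restriction under missing values and outliers. Its specific missing-data rules concern event dates: imputing an incomplete date, and right-censoring. The sections on PSA (8.4.3.1.1), soft tissue response (8.4.3.1.2) and CTC response (8.4.3.1.10) do not say how a patient without an assessment is counted.

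Section 8.2 sets up a Simon two-stage test for the mutation-negative cohort: "The null hypothesis that the true PSA response rate is 5% will be tested against a one-sided alternative". It says that "in the first stage, 23 subjects will be enrolled" and that "If there are one or fewer PSA responses in these 23 subjects, the study will be stopped". Rejection needs at least six responses in 56 patients, with a stated significance level of 0.05 and power of 80% at a true rate of 15%.

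Section 4.5 adds, without limiting it to Part 1: "The sponsor will decide if patients who prematurely discontinue will be replaced".

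**The concern.** The two rules cannot both govern a response rate. A patient who was never evaluated belongs to the ITT denominator under 8.3 and is not an observed case under 8.4. The conflict matters most for patients who stop or die before a post-baseline assessment, because they have no recorded response. Leaving them out moves the rate in one direction only.

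Section 8.2 says that the enlarged cohorts are meant to give a more accurate PSA response estimate in support of the phase 3 design. A rate computed among patients who stayed long enough to be assessed answers a different question from the rate among all who started.

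The formal test is also exposed. Section 8.2 speaks of enrolment for the first 23 but only of patients for the 56, and does not say whether a replacement counts towards either. In an open-label study this should be settled before responses are known.

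**Working it through.** **Direction of the effect on the estimate.** Let N be the patients enrolled, M those without an assessment and R the observed responders. ITT with missing as non-response gives R/N; observed cases give R/(N − M). The second is never smaller, and is larger whenever M > 0 and R > 0. Illustrations, with M assumed:

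- N = 56, R = 6, M = 0: 6/56 = 10.7%
- M = 6: 6/50 = 12.0%
- M = 11: 6/45 = 13.3%

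**The stated design (section 8.2).** Inputs: stage 1 n = 23, stop at 1 or fewer responses; total n = 56, so 33 more in stage 2; reject at 6 or more; null rate 5%, alternative 15%. The exact probability of rejection at true rate p is

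P(reject | p) = Σ over x = 2 to 23 of P[Bin(23, p) = x] × P[Bin(33, p) ≥ 6 − x].

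- p = 0.05: 0.04996, with probability 0.679 of stopping at stage 1
- p = 0.15: 0.8003, with probability 0.120 of stopping at stage 1

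Both stated figures reproduce.

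**Case A: 23 and 56 are enrolled patients, none replaced.** The rule counts responses. Removing a non-evaluable patient from a denominator adds no response, so alpha at an all-enrolled rate of 5% stays 0.050 and power at an all-enrolled rate of 15% stays 0.800. Only the reported percentage changes.

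**Case B: drop-outs are replaced until 23 and then 56 are evaluable, or only evaluable patients are counted up to those numbers.** Assume that a share m of enrolled patients is non-evaluable and that all of them are non-responders. A true all-enrolled rate of 5% then becomes 0.05/(1 − m) per counted patient. Putting this into the same formula:

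| Assumed m | Rate per counted patient | Alpha |
|---|---|---|
| 0% | 0.0500 | 0.050 |
| 5% | 0.0526 | 0.061 |
| 6.7% (4/60: 60 enrolled to obtain 56) | 0.0536 | 0.065 |
| 10% | 0.0556 | 0.075 |
| 15% | 0.0588 | 0.092 |
| 20% | 0.0625 | 0.114 |

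The protocol gives no non-evaluable share for Part 2, so m is an assumption throughout.

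**The case against.** The strongest reply is that this is ordinary SAP material. Sections 8.3 and 8.4 defer data-set criteria and detailed methods to the SAP, which is not shown, and observed cases only may mean no more than that values will not be imputed. That would be decisive if the protocol left missing responses open. It does not: it fixes the observed-case rule twice and for all evaluations. An SAP that counted missing as non-response would depart from the protocol, and one that followed the protocol would defeat the ITT definition.

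Part of the reply stands. CTC response requires a zero count at week 12, so a patient without that sample cannot be a responder; only the denominator is in doubt. PSA and ORR include best response, PSA is first measured at week 2 in Part 2, and discontinued patients are invited to an end-of-study visit that includes PSA. The missing share for PSA may therefore be small.

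A reader might infer four stronger things that the documents do not support.

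- *That the two-stage test loses its error rate outright.* The observed-case rule alone does not do this (Case A). Section 8.2 uses the word enrolled for the first 23, and replacement is only a sponsor option.
- *That power falls.* This depends on what the 15% refers to. As an all-enrolled rate, power stays at 80% in Case A. As a rate among evaluable patients with none replaced, the test becomes conservative: at m = 10%, alpha is 0.033 and power 0.715. That is a question about the design rate, and counting missing as non-response would not change it.
- *That Part 1 supplies the missing share.* Section 1.1.1 reports "A total of 6 out of 31 (19.4%) evaluable patients had a PSA response", out of 38 treated. It does not say why seven were not evaluable, mixes dose levels, and comes from an August 2020 cut-off of an ongoing study.
- *That the 8-week condition in section 8.5 and the PP definition also remove early failures.* Section 8.5 times the interim look; section 8.2 defines the stage-1 patients. PP, defined as "Patients who have completed the study according to the protocol without relevant major protocol deviations", is secondary with criteria left to the SAP, and a patient who progresses early can still have followed the protocol to the end.

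**Conclusion.** The contradiction between sections 8.3 and 8.4 is in the current text and should be resolved. Read literally, section 8.4 gives PSA, ORR and CTC0 rates at or above the ITT rate, and above it whenever anyone is missing and at least one patient responds. The direction is certain against the benchmark in which a missing assessment is a non-response. The size depends on a missing share that the protocol does not state; with six of 56 missing and six responders it is 10.7% against 12.0%.

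The error-rate point is conditional and concerns only the mutation-negative cohort, the one with a formal test. Alpha stays at 0.050 if 23 and 56 are enrolled patients. It rises to 0.061, 0.075 or 0.114 at an assumed 5%, 10% or 20% non-evaluable only if drop-outs are replaced or evaluable patients alone are counted, and if the non-evaluable are non-responders.

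**What to change.** In section 8.4, exempt binary response endpoints from the observed-case rule. In the ITT analysis, a missing PSA, RECIST or CTC assessment counts as non-response. For ORR the denominator is patients with measurable disease at baseline; for CTC0 it is patients with a nonzero baseline count. Keep observed-case rates as a supportive table.

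In sections 8.2 and 8.5, define the 23 and the 56 as the first enrolled mutation-negative patients, assessed or not, with no replacement within the test. Section 4.5 can keep its general replacement option if it refers to this exception. With these definitions, and with 5% and 15% read as rates among all enrolled patients, the stated alpha of 0.050 and power of 0.800 hold.

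The cost is wording in these sections and slightly lower reported response rates. No new data are needed. The change should be in place before the stage-1 look.

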## 8.4.1 Demographic and other baseline characteristics

All relevant demographic and baseline characteristics will be summarised using descriptive statistics. The number and reasons for discontinuations will be listed and tabulated by treatment groups.

An authorised person will code medical history and concomitant diseases using standard coding dictionaries.

#### 8.4.2 Treatment compliance and extent of exposure

The number of patients exposed to ODM-208 and corticosteroid replacement treatments, and dose and the duration of exposures will be tabulated with descriptive statistics.

#### 8.4.3 Analysis of efficacy

#### 8.4.3.1 Analysis of antitumour effects

#### 8.4.3.1.1 PSA

PSA data will be analysed descriptively by dose. Best response and the number of responders (30% and 50% decline from baseline) will be presented, and percentage of change from baseline will be tabulated by time point and by dose.

#### 8.4.3.1.2 Soft tissue response

The frequency of responders according to RECIST 1.1 (Eisenhauer EA et al., 2009) of soft (target and non-target) lesions will be presented. ORR will be presented by time point. ORR is defined as best objective response of complete response (CR) or partial response (PR) by RECIST 1.1. Descriptive statistics of sum of lesion diameters and percent changes will be presented.

#### 8.4.3.1.3 Bone

Bone progression by PCWG3 (Scher HI et al., 2016) and the changes from baseline in the number of lesions on bone scan will be reported as "no new lesions" or "new lesions".

#### 8.4.3.1.4 ECOG performance status

The ECOG performance status and the changes from baseline will be summarised with descriptive statistics. Time to ECOG deterioration will be measured from enrolment to deterioration of ECOG >1 point. Patients who do not experience event or die will be censored.

Time to ECOG deterioration will be summarised with descriptive statistics and Kaplan-Meier method.

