#### Variables and methods of assessments

#### Assessment of antitumour effects:

PSA: Serum total prostate specific antigen (PSA) concentrations will be determined. PSA response or progression will be evaluated using the Prostate Cancer Working Group 3 (PCWG3) criteria.

Soft tissue response: Chest, abdomen and pelvic computed tomography (CT) or magnetic resonance imaging (MRI) will be performed. Changes in tumour burden will be assessed using the Response Evaluation Criteria In Solid Tumours (RECIST) 1.1. Objective response rate (ORR) i.e. the rate of complete (CR) and/or partial responses (PR) by RECIST 1.1 will be assessed.

Bone: Radionucleotide bone scans will be performed. The status of bone metastases will be assessed using the PCWG3 criteria.

ECOG performance status: ECOG performance status will be assessed. Time to ECOG performance deterioration will be assessed.

Clinical disease progression: Assessment of the disease progression during the study will be based on PSA, imaging and clinical status, and it is characterised by e.g. a decrease in patient's ECOG score, clinically significant loss of appetite, weight loss (more than 10% from baseline), or increase in pain. The decision regarding disease progression is made by the investigator based on available data.

Time to PSA progression will be assessed according to the PCWG3.

Time to radiographic progression will be assessed by either RECIST progression and/or progression on bone scan by PCWG3.

Duration of objective response will be assessed.

Radiographic progression-free survival (rPFS) by either RECIST progression and/or progression on bone scan by PCWG3.

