## Figure 1. Overall study design

\*Includes Group 1 and Group 2

#Total includes 45 AR mut+ subjects already enrolled in Part 2. (added in Amendment 12)

**Part 1/Phase 1** of the study consists of a screening period of maximum 21 days, a treatment period for each patient lasting as long as it is considered beneficial to the patient (as judged by the investigator) or until death, intolerable toxicity, or any other discontinuation criteria is met, and a post-treatment period (28 days). If needed, adrenal recovery will be followed after the end-of-study visit (EOS) (for a maximum of 24 weeks) (added in Amendment 3). In addition, the study consists of an optional pre-screening period for a mutation analysis of the AR gene.

While on study treatment, patients will visit the site once a week for the first 4 weeks, every 2 weeks from week 4 to week 12, every 4 weeks from week 12 to week 24, and thereafter every 12 weeks until discontinuation of study treatment. Weekly telephone contacts (TCs) are included for the first 4 weeks. During the post-treatment period after the discontinuation of the ODM-208 treatment, adrenal recovery of the patients will be followed by weekly visits until EOS. If the

patient is still on corticosteroid replacement therapy at EOS visit, adrenal recovery of the patient will be followed by a visit at 4 weeks and, if needed, at 8 weeks. If replacement therapy still needs to be continued beyond 8 weeks after the EOS, the patient will be contacted by a phone call at 16 weeks and, if needed, at 24 weeks after the EOS. Visit schedule for Part 1 is presented in Figure 2. The DLT period in Part 1 is 28 days (section 3.3.4).

**Part 2/Phase 2** of the study consists of a pre-screening period  $(\leq 3 \text{ months prior to screening start})$  for centralized analysis of the AR LBD mutations in plasma ctDNA, a screening period of maximum 21 days, a treatment period for each patient lasting until disease progression or until death, intolerable toxicity, or any other discontinuation criteria is met. The treatment may be continued after disease progression if the patient is considered to clinically benefit from the treatment as judged by the investigator. The study contains a post-treatment period (28 days), and if needed, adrenal recovery will be followed after the end-of-study visit (EOS) (for a maximum of 24 weeks).

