While on study treatment, patients will visit the site once a week for the first 4 weeks, every 2 weeks from week 4 to week 12, every 4 weeks from week 12 to week 24, and thereafter every 12 weeks until discontinuation of study treatment. Telephone contacts (TCs) are included for the first 7 weeks. During the post-treatment period after the discontinuation of the ODM-208 treatment, adrenal recovery of the patients will be followed by a visit taking place 2 weeks after the treatment discontinuation. The EOS visit takes place 4 weeks after the discontinuation of the ODM-208. If the patient is still on corticosteroid replacement therapy at EOS visit, adrenal recovery of the patient will be followed by a visit at 4 weeks and, if needed, at 8 weeks. If replacement therapy still needs to be continued beyond 8 weeks after the EOS, the patient will be contacted with a phone call at 16 weeks and, if needed, at 24 weeks after the EOS. Patient survival status will be checked at least every 12 weeks, by telephone, e-mail, chart review, or review of public records, in compliance with local practices or regulations, for up to 2 years after the EOS visit for the final patient. Visit schedule for Part 2/Phase 2 is presented Figure 3.

Figure 2. Visit schedule for Part 1/Phase 1.

Adrenal Pre Post-treatment period recovery Screening Treatment period Screening followup Glucocorticoid .... Fludrocortisone Screening Survival visit 13+ 5 End-ofvisit follow-up Post-treatment study v /isit /isit Visit Visit Visit ∕isit Visit /isit Visit /isit Visit visit Within 21 Day Day Day 15 Day 22 Day Week Week Week Week Week Week Week Week +14 28 days 10 12 16 20 after the days 24 days last ODM-208 TC = telephone contact dose \*added in Amendment 12 Adrenal Pre-Post-treatment recoverv Screening Treatment period Screening period followup Glucocorticoid Fludrocortisone .... Screening ÷ visit 0 2 ost-treatment /isit Visit study /isit /isit End-Visit Visit Visit 0 Visit Visit Visit Visit Visit C visit Within 21 Day Day Day Day Day Week Week Week Week Week Week Week +14 28 davs Week days 29 10 12 16 20 24 36+ after the days last ODM-208 TC = telephone contact dose

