# 3.3.7 Definitions of tumour response and disease progression

Assessment of disease progression during the study will be based on PSA, imaging and clinical status. A change in tumour burden will be assessed using the Response Evaluation Criteria In Solid Tumours (RECIST) 1.1 (Eisenhauer EA et al., 2009). Status of bone will be assessed using

the Prostate Cancer Working Group 3 (PCWG3) criteria (Scher HI et al., 2016). PSA response and progression will be evaluated using the PCWG3 criteria.

Clinical disease progression is characterised by e.g. an increase in patient's Eastern Cooperative Oncology Group (ECOG) score, clinically significant loss of appetite, weight loss (more than 10% from baseline), or increase in pain and it refers to cases where the clinical deterioration of a patient is judged to be due to tumour progression that cannot be documented using objective methods. Such cases should be carefully differentiated from disease-related AEs, ODM-208related and corticosteroid-associated symptoms and signs. The decision regarding disease progression is made by the investigator based on available data.

Part 2/Phase 2 only: CTC response is defined as CTC count nonzero at baseline and 0 at 12 weeks (CTC0) (Heller G et al., 2018).

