# 4.2 Inclusion criteria

Subjects must meet all of the following criteria to be eligible for the study:

- 1. Written informed consent (IC) obtained.
- 2. Males aged  $\geq$  18 years.
- 3. Life expectancy > 3 months.
- 4. ECOG performance status 0-1.
- 5. For Part 1/Phase1: Histologically confirmed adenocarcinoma of the prostate without neuroendocrine differentiation or small cell features. For Part 2/Phase 2: Histologically confirmed adenocarcinoma of the prostate without pure small cell features.
- 6. Metastatic disease documented either by a positive bone scan, CT, PET/CT or MRI scan.
- 7. Castration-resistant prostate cancer with serum testosterone < 50 ng/dl (< 0.5 ng/ml, < 1.7 nmol/l).
- 8. Patients must maintain ongoing androgen deprivation therapy with a gonadotropin-releasing hormone (GnRH) analogue (agonist or antagonist) or have had bilateral orchiectomy.

- 9. For Part 1/Phase 1: Treatment with at least 1 line of chemotherapy or ineligibility for chemotherapy. For Part 2/Phase 2: Treatment with at least 1 line of taxane-based chemotherapy in castration-sensitive prostate cancer (CSPC) or in CRPC.
- 10. Treatment of at least 1 line of novel AR targeted hormonal therapy in CSPC or in CRPC for a minimum of 12 weeks (e.g. abiraterone, enzalutamide, darolutamide, apalutamide).
- 11. [Obsolete inclusion criterion removed in Amendment 7.]
- 12. Documented disease progression by one or more of the following criteria:
  - PSA progression defined by a minimum of 2 elevated PSA levels with an interval of at least 1 week between the measurements. The PSA value at the screening visit should be ≥ 1 ng/ml (For Part2/Phase 2), ≥ 2 ng/ml (for Part 1/Phase1).
  - soft tissue disease progression as defined by RECIST 1.1 criteria.
  - bone disease progression as defined by PCWG3 criteria.

13. Adequate marrow, liver and kidney function.

- haemoglobin  $\ge 10$  g/dl (in absence of blood transfusion within 7 days of value obtained)
- absolute neutrophil count (ANC)  $\geq 1500/\mu l (1.5 \times 10^{9}/l)$
- platelet count  $\geq 100\ 000/\mu l\ (100\ x\ 10^9/l)$
- aspartate aminotransferase (AST) and alanine aminotransferase (ALT)  $\leq$  3 x upper limit of normal (ULN) ( $\leq$  5.0 x ULN if liver metastases present)
- total bilirubin  $\leq 1.5 \text{ x ULN}$  (< 3 ULN if Gilbert's syndrome)
- albumin  $\geq 3.0 \text{ g/dl}$
- creatinine clearance  $\geq 60$  ml/min using serum creatinine

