# 6.2.1.4 ECOG performance status and clinical progression

ECOG performance status will be assessed at every visit during ODM-208 treatment (see section 6.1).

Clinical progression will be assessed. See 3.3.7 for details in definition of clinical progression.

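### ECOG is not read after ODM-208 stops, so time to ECOG deterioration is likely to be informatively censored; separately, the synopsis and section 3.3.7 give opposite ECOG directions for clinical progression

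*Protocol*

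**What the plan says.** **Event and censoring.** Section 8.4.3.1.4 defines the endpoint: "Time to ECOG deterioration will be measured from enrolment to deterioration of ECOG >1 point". It continues: "Patients who do not experience event or die will be censored". The same section also provides for descriptive summaries of ECOG status and of its change from baseline. Section 4.2 admits patients with "ECOG performance status 0-1".

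**When ECOG is read.** Section 6.2.1.4 says "ECOG performance status will be assessed at every visit during ODM-208 treatment". In Tables 2 and 3 the ECOG row runs from screening to Visits 13, 14 etc. and then stops. It has no entry at the post-treatment visits, EOS or adrenal follow-up. The EOS procedure list in section 6.1.6.2 includes a physical examination, weight, vital signs, ECG and PSA, but not ECOG. Section 3 gives the later visit spacing as "every 4 weeks from week 12 to week 24, and thereafter every 12 weeks until discontinuation of study treatment".

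**What ends treatment.** Section 4.5 lists investigator-judged progression among the reasons for stopping, with an allowance to continue. For Part 2, section 3 says "The treatment may be continued after disease progression if the patient is considered to clinically benefit".

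**Direction of ECOG change in clinical progression.** The synopsis says of progression that "it is characterised by e.g. a decrease in patient's ECOG score". Section 3.3.7 says "Clinical disease progression is characterised by e.g. an increase in patient's Eastern Cooperative Oncology Group (ECOG) score".

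**The concern.** A Kaplan-Meier estimate is unbiased only if censored patients have the same later risk of the event as those still being observed. Here observation of ECOG ends with treatment. One of the usual reasons for ending treatment is that the patient is getting worse, so patients censored at that moment are unlikely to resemble those who carry on. If their deterioration would have been recorded soon afterwards, the curve stays too high and the reported time is too long.

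A statistical analysis plan can refine an event definition or a censoring date. It cannot recover a reading that the schedule of events never asked for, so the matter belongs in the protocol.

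The conflict over ECOG direction is a different kind of defect. It concerns a listed sign of clinical progression, which in turn feeds the decision to stop treatment.

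**Working it through.** The protocol states no figure for this endpoint, so there is nothing to reproduce. The check sets the sections side by side and adds one illustration.

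**1. Threshold.** On a whole-number scale, a worsening of more than 1 point is a worsening of at least 2.

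| Entry ECOG | Counts as event | Does not count |
|---|---|---|
| 0 | 2 or higher | 0 to 1 |
| 1 | 3 or higher | 1 to 2 |

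**2. Length of the blind interval.** After week 24, ECOG visits fall on Day 169, Day 253, Day 337 and so on. The spacing is 253 − 169 = 84 days, or 12 weeks. A patient who stops just before a scheduled visit may have a last ECOG reading nearly 12 weeks old. EOS follows 28 days (4 weeks) after the last dose. If ECOG is not read there, up to about 12 + 4 = 16 weeks between the last reading and EOS go unobserved, before allowing for visit windows.

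**3. Link between stopping and the event.** Section 3.3.7 names an ECOG rise as one example of clinical progression, and section 4.5 makes progression a reason to stop. Worsening performance can therefore contribute to ending the only period in which the endpoint can be observed. This makes independent censoring doubtful, and the expected direction is towards a longer estimated time.

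**4. How much censoring could there be?** This is an illustration only. Assume independent exponential times, with stopping hazard h_d = 1/4.8 = 0.208 per month. The 4.8 months is the mean time on treatment of Part 1 mutation-positive patients in the Clinical Data section, where 8 such patients were evaluable for PSA response. The table of contents does not list that section, so the figure serves only to set a scale. The median time m to a qualifying worsening is **assumed**, with h_e = ln 2 / m. The share censored by stopping is h_d / (h_d + h_e).

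| Assumed median m (months) | h_e | Share censored by stopping |
|---|---|---|
| 3 | 0.231 | 47% |
| 6 | 0.116 | 64% |
| 9 | 0.077 | 73% |
| 12 | 0.058 | 78% |
| 18 | 0.039 | 84% |
| 24 | 0.029 | 88% |

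The result runs from just under half to nearly nine in ten, driven by an input the protocol does not give. It also measures the amount of censoring, not the bias: under the independence assumed here, Kaplan-Meier would be unbiased. The bias depends on how strongly stopping and worsening are linked, and nothing in the protocol quantifies that.

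**5. Direction conflict.** The synopsis and section 3.3.7 describe the same concept with opposite signs. Section 8.4.3.1.4 speaks only of deterioration and does not draw on the synopsis sentence, so this conflict does not affect the endpoint in steps 1 to 4.

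**The case against.** The strongest reply has five parts.

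- **Progression is not automatic after a 1-point rise.** This stands. Section 3.3.7 gives an ECOG rise as an example, requires tumour-related deterioration to be separated from adverse events and steroid effects, and leaves the decision to the investigator. Treatment, and with it ECOG reading, may continue after progression. A reader might infer that the typical patient worsens by one point, is taken off drug and never has the chance to reach two. The text shows only that this path is possible.
- **One-point changes are reported anyway.** This stands. Section 8.4.3.1.4 summarises changes from baseline, so shifts of 0 to 1 and 1 to 2 on treatment remain visible.
- **A 2-point threshold is a legitimate choice.** This stands. It is stricter and less noisy, and no section defines deterioration as 1 point. Confirming the intention is reasonable; calling the threshold wrong is not.
- **Censoring details belong to the statistical analysis plan.** This stands in part. Section 8.4 defers detailed methods there, and the sentence on death in section 8.4.3.1.4 can be read two ways, so it should not be taken as settled that deaths are censored. The absence of an ECOG reading at EOS is fixed by the protocol's own schedule.
- **A later ECOG reading has its own problems.** This stands as a cost. At EOS, performance may reflect steroid tapering and adrenal recovery as well as tumour.

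**Conclusion.** The point holds, and it is minor. The protocol ends ECOG reading with treatment, leaves gaps of up to 12 weeks before that, and needs a 2-point worsening for an event. Censoring at discontinuation is therefore likely to be informative, with bias towards a longer time to deterioration. This rests on the assumption, reasonable but not demonstrated in the protocol, that patients who stop are worsening faster than those who continue.

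Two stronger conclusions are tempting and not supported. A reader might infer that real deterioration is mostly censored; without an ECOG event rate that cannot be said, and the illustration falls below half at its fast end. A reader might also tie the synopsis wording to the censoring; the two are unrelated.

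The consequences are limited. No objective names ECOG deterioration, section 8.1 sets no formal hypotheses, and the two-stage rule in section 8.2 rests on PSA response. The direction conflict needs reconciling in its own right because it touches a sign that feeds treatment discontinuation.

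**What to change.** 1. **Add ECOG at EOS** in Table 3 and section 6.1.6.2, for patients who have not yet reached that visit. Include the reading in time to ECOG deterioration, and report the on-treatment-only version as a sensitivity analysis.
2. **Confirm the threshold.** State in whole points whether at least 2 is intended. A 1-point version may be shown as supportive. In the same sentence, make clear how death is handled.
3. **Reconcile the synopsis with section 3.3.7** on the direction of ECOG change in clinical progression.

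**Cost.** One table entry and one list item at a visit that already includes a physical examination, plus wording edits. The main drawback is uneven ascertainment. The Figure 1 footnote says 45 mutation-positive patients were already enrolled in Part 2 at Amendment 12. If all were past EOS, 45/60 = 75% of that planned cohort would lack the reading; the true number is not given. Mutation-negative patients enter Part 2 only under Amendment 12 and could all have it. Any side-by-side display by mutation status should therefore rely on the on-treatment-only version. The possible influence of adrenal recovery on EOS ECOG should be noted when results are reported.
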